### The following documents are currently attached to this item:

There are no documents attached for this item.

# **Subject Confidentiality**

There will be no paper-based records kept for this study. Computer-based files will only be made available to personnel involved in the study through the use of access privileges and passwords. Prior to access to any study-related information, personnel will be required to sign statements agreeing to protect the security and confidentiality of identifiable information. Whenever feasible, identifiers will be removed from study-related information. Precautions are in place to ensure the data is secure by using passwords and encryption, because the research involves web-based surveys. The information that will be collected include responses to health questionnaires, responses to ease of use questionnaires, and data on how participants engage and use content in the platform. This de-identified information will be seen by the people involved with this research. Steps will be taken to protect participants identity through de-identifying information, and information collected will be kept secure. All information collected will be protected by HIPAA (Health Insurance Portability and Accountability Act), this is the law that protects participants personal health information. To do this study, we need to collect and analyze participant data. This will be done by personnel at University of Pennsylvania and NeuroFlow, Inc. for the purpose of this research, data will not be shared outside these two entities. The identifying information that will be collected includes participant first and last name, email, phone number and date of birth (which is needed in order to set up participant accounts), and Qualtrics survey responses with other demographic information. We will also have an excel sheet that contains identifying data in connection to assigned participant ID. These identifying data will be kept in a password protected excel sheet which will be stored in Penn Box and kept separate from study data. In order to de-identify data,

we will take a participants assigned participant ID number in place of any identifying data which will be connected to their deidentifying data (detailed below). De-identified study data that includes baseline assessment and post app usage assessment results via the Neuroflow application will be collected about participants for this study. For people who consented to have their contact information on file for future research, we will store it in a password protected excel sheet. For other participants, all identifying data will be destroyed within one year from their participation end date. The information from this study may be published in scientific journals or presented at scientific meetings, but participants will not be personally identified. participant private information, with the identifiers removed, could be used for future research studies or distributed to other researchers for future research studies without participants additional permission

#### Sensitive Research Information\*

Does this research involve collection of sensitive information about the subjects that should be excluded from the electronic medical record? [NOTE: This does not apply to: 1) research information that would not normally be included in the electronic medical record or 2) information that is in the electronic medical record as part of clinical care.]

No

#### **Disclosures**

Will any data or specimens from Penn participants OR other research generated work product (e.g., intellectual property) be disclosed to any individuals, entities, or vendors, etc. outside of Penn?

No

#### Data Protection\*

x Name

Street address, city, county, precinct, zip code, and equivalent geocodes

All elements of dates (except year) for dates directly related to an individual and all ages over 89

- x Telephone and fax number
- x Electronic mail addresses

Social security numbers

Medical record numbers

Health plan ID numbers

**Account numbers** 

Certificate/license numbers

Vehicle identifiers and serial numbers, including license plate numbers

Device identifiers/serial numbers

Web addresses (URLs)

**Internet IP addresses** 

Biometric identifiers, incl. finger and voice prints

Full face photographic images and any comparable images

Any other unique identifying number, characteristic, or code

None

Does your research request both a waiver of HIPAA authorization for collection of patient information and involve providing Protected Health Information ("PHI") that is classified as a "limited data set" (city/town/state/zip code, dates except year, ages less than 90 or aggregate report for over 90) to a recipient outside of the University of Pennsylvania covered entity?

No

# Consent

# 1. Consent Process

#### Overview

Participants will receive a brief introduction to study via the description section of the SONA system or via the flyers that will be distributed for recruitment. Participants will all need to contact the study team via SONA or other methods of recruitment to express interest in participating before any next steps commence. All participants will have access to a brief introduction of the study aims and objectives via the first page of the mandatory Qualtrics form that must be filled out in order for study participation as well. In both cases, participants will be required to sign up for a 15 minute check in and check out meeting before and after the trial to answer participant questions regarding the app/app set up or concerns about the consent form. Informed consent will take place digitally for this study. An outline of the Qualtrics form is that, after providing a brief introduction of the study, participants will be prompted to fill out a consent to contact form and a brief demographics survey before being presented with a consent form. After reading through it, participants will have to select I have read the above terms and consent to participate in this study before they will be eligible to continue with the study. Participants will be informed that they can withdraw from the study at any time without any consequences by emailing the PI or any other researchers affiliated with the study. The consent form will be written in comprehensible language and we expect all participants to be able to give their own consent. Participants will not receive an invitation to the NeuroFlow platform until they have consented to participate in the study.

# Risk / Benefit

### **Potential Study Risks**

We anticipate very few risks associated with participating in the study. Participants may feel uncomfortable answering certain questions, but all questions will be optional and there will be no penalties or consequences associated with choosing to opt out of providing certain information. As with any study taking personal information, there is the risk of a possible data breach that could expose information about participants mental health, However, we will be deidentifying our dataset and any datasets with identifying information will be password locked. Only study personnel will have access to any data associated with the study. In the event of a mental health crisis or reports of suicidal ideation, the NeuroFlow platform lists emergency resources within the app.

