#### **Procedures**

This study is a two-arm pilot randomized controlled trial to assess differences in user retention and usage rates associated with two incentive structures within the NeuroFlow app (I.e., general structure versus financial compensation). We will assess user engagement with utilization data (ie., daily, weekly, and monthly active users) and measures of the total number of activity counts completed by a user. After consenting to participate in the study, participants will be randomly assigned to use Neuroflow either with points only or with points and the opportunity to exchange those points for gift cards. In both conditions, participants will begin by completing a consent form and a brief questionnaire with their contact information, which will be used to grant them access to the Neuroflow platform. In both recruitment methods, participants will be required to sign up for a 15 minute check in and check out meeting before and after the trial to answer participant questions regarding the app/app set up or concerns about the consent form. Furthermore, a Qualtrics survey will also be dispersed to participants to be taken during this time along with an initial baseline assessment (to be administered in the NeuroFlow app). Baseline and post-app usage Qualtrics survey links will also be sent with measures

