(Generalized anxiety disorder (GAD), Patient Health Questionnaire (PHQ), World Health Organization-Five Well-Being Index (WHO-5), and Difficulties in Emotion Regulation Scale (DERS)) to participants in order to assess differences in user retention. In both conditions, participants will use the Neuroflow app throughout the duration of the 4-week study (28 days). Participants will be sent a push notification each day through the app to complete their daily activities, which could include surveys, videos, or skill-based practice materials. With the collaboration of the Neuroflow team, the usage metrics of the app will be pulled after the end of the study. The user metrics of interest are identifying factors that include first name, last name, gender, age, date of birth, and the applicable assignments to each participant - care team manager and behavioral health specialist. Additionally, the first and last score, first and last date, and time between the first and last assessment dates for the measures of interest (PHQ-9, GAD-7, WHO-5, DERS). Furthermore, the total activity number and the total activity rate across all measures will be collected. No additional data from or about participant phone usage or activities will be pulled as part of the study other than the usage metrics specified above, specific to Neuroflow.

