### **Analysis Plan**

The anticipated statistical analyses to be conducted for this study is a Linear-mixed effects model (LMMs). These models will be used to examine the effect of different incentives (behavioral economics and financial vs. behavioral economics only) on user engagement (measured by the number of active users, the number of activities completed, and completion of daily mood and sleep ratings) and retention. We will also examine the effect of incentive type on secondary mental health outcomes such as anxiety symptoms (GAD-7total score), depression symptoms (PHQ-9 total score), wellbeing (WHO-5total score)and emotion regulation (DERS total score).

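### No response is described for suicidal ideation reported in the two Qualtrics surveys; the only provision is a resource list inside the separate app

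*Combined protocol and SAP*

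**What the plan says.** Procedures describes two Qualtrics contacts: "Baseline and post-app usage Qualtrics survey links will also be sent with measures". The list of measures that follows includes the PHQ, along with anxiety, well-being and emotion-regulation scales. A survey is also to be completed around the meetings: "Furthermore, a Qualtrics survey will also be dispersed to participants to be taken during this time along with an initial baseline assessment", the latter being given in the app. Both Procedures and the Consent overview describe the required 15-minute meetings as a check-in and "check out meeting before and after the trial to answer participant questions regarding the app/app set up or concerns about the consent form".

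The Analysis Plan uses the PHQ-9 only as a total score, for a secondary outcome. General Attachments lists a PHQ-9 file.

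On reported ideation, Potential Study Risks has one sentence: "In the event of a mental health crisis or reports of suicidal ideation, the NeuroFlow platform lists emergency resources within the app". The same section makes every question optional.

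Subject Confidentiality says that the identifying information collected "includes participant first and last name, email, phone number and date of birth". It adds that a password-protected file connects identities to participant IDs and is stored apart from the study data. It also describes the health-questionnaire responses seen by the research team as de-identified.

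**The concern.** The protocol foresees that ideation may be reported, but it places its response in a different system from the one that collects two of the PHQ administrations. A participant who endorses the ideation item in Qualtrics gets help, on the text supplied, only by opening NeuroFlow and finding the list.

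That provision is weakest for people who have stopped using the app. The Background says that mental health apps often fall short because users do not stay engaged, and retention is a primary question of this trial. The second survey comes after the 28 days of use, when some participants may no longer be opening the app.

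What is at stake is participant safety. The comparison of incentives does not depend on this point.

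**Working it through.** There is no figure in the plan to reproduce. The check sets the relevant sections side by side and then sizes the work.

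**What is described for a Qualtrics answer**

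| Question | Section | What it gives |
|---|---|---|
| Where is the PHQ given? | Procedures | Qualtrics, at baseline and after app use |
| What are the meetings for? | Procedures; Consent overview | App set-up and consent questions |
| How are PHQ-9 answers used? | Analysis Plan | Total score as a secondary outcome |
| What follows reported ideation? | Potential Study Risks | A resource list inside the app |
| Could staff reach the participant? | Subject Confidentiality | Yes, through the ID file and contact details |

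No supplied section describes a reviewer of the ideation item, an alert, a response time, a referral, or a resource message within Qualtrics. The form heading on suicidal ideation and behavior, under Study Procedures, is a general question about drug or biological test articles and sets no procedure.

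**Number of submissions**

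- Inputs from the documents: 100 participants (Subjects enrolled by Penn Researchers) and two surveys (Procedures).
- Maximum: 100 × 2 = 200.
- If an assumed 70% complete the second survey: 100 + 70 = 170.

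**Positive answers, for sizing the work only**

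- Assumed 1% to 10% of submissions: 170 × 0.01 = 1.7, up to 200 × 0.10 = 20.
- These count submissions, so one person may count twice.

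**Staff time**

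- Checks at an assumed 1 to 2 minutes each: 170 × 1 = 170 min = 2.8 h, up to 200 × 2 = 400 min = 6.7 h.
- Share of a 15-minute meeting: 1/15 = 7% to 2/15 = 13%.
- Referrals at an assumed 15 to 30 minutes each: 1.7 × 15 = 25.5 min = 0.4 h, up to 20 × 30 = 600 min = 10 h.
- Total: 170 + 25.5 = 195.5 min = 3.3 h, up to 400 + 600 = 1,000 min = 16.7 h.

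**The case against.** **Documents that were not supplied.** General Attachments lists the consent form, the screener, the app's terms of service and the PHQ-9. The consent form is a natural place to say who sees answers and what follows a report of ideation. This stands as a limit: a reader might infer that the trial has no ideation procedure at all, and the supplied text cannot show that.

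**A care team may exist.** Procedures names a "care team manager and behavioral health specialist" among the assignments to be extracted for each participant, and PHQ-9 scores are also drawn from the app. A reader might infer that in-app answers go unreviewed. The documents do not settle this either way: the roles appear only as data fields, with no stated duty to review or respond. If in-app answers are reviewed, the remaining gap is smaller, but nothing links that team to Qualtrics.

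**De-identification.** A reader might infer that staff see ideation answers next to names and do nothing. That is not supported. Subject Confidentiality treats health-questionnaire responses as de-identified. Its mention of Qualtrics responses among identifying data may refer to the consent and demographics form. What the text does support is that answers can be linked through the ID file.

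**Proportion.** This is an exempt pilot in adult students, every question is optional, and some resource provision exists. Optional questions protect those who skip the item but offer nothing to those who answer it. The objection that staff review alone is a heavier remedy than needed is fair: an automatic message in Qualtrics costs almost nothing and keeps answers de-identified, so it belongs first in the fix.

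**Conclusion.** The point holds in limited form. On the supplied text, the only described response to reported ideation is a passive list inside the app, and nothing is tied to the PHQ answers given in Qualtrics. This covers at most 200 submissions, or 170 at the assumed completion rate. The number that would be positive is unknown.

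The conclusion assumes that the Qualtrics PHQ is the attached PHQ-9 and carries its usual ideation item. That is reasonable, since the Analysis Plan and General Attachments both name the PHQ-9, but the items are not printed. It also remains open to correction by the unsupplied attachments, so confidence is medium.

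Two further inferences should be resisted: that the surveys themselves raise risk, and that the incentive result is compromised. Nothing in the documents supports either. The change should be made because the protocol already expects such reports and the remedy is small.

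**What to change.** Revise Procedures and Potential Study Risks as follows.

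1. **Automatic message.** Set both Qualtrics surveys to show crisis and counselling resources at once to anyone who endorses the ideation item. Include resources open to students outside Penn, since Target population and Participant recruitment allow them. This needs almost no staff time and no identification.
2. **Staff check and referral.** Have an existing study team member check that item around the check-in and check-out meetings, or within one working day if the survey arrives later. Use the ID file and contact details already held to offer a direct referral to anyone who endorses it. Do not pursue a skipped item.
3. **Disclosure.** Amend Subject Confidentiality and the consent form to say that this one item is checked in linkable form, and when.

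If an attachment already sets such a procedure, Potential Study Risks should state it.

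**Cost.** About 3 to 17 staff hours over the trial under the assumptions above, plus a short referral script, a staff briefing and the wording changes. The estimate leaves out repeated contact attempts and any clinician back-up. The check may not always fit within the 15-minute meeting.

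**Downsides.** Staff view one item in linked form. Candour on a secondary outcome may fall slightly, which should be equal in both arms. One working day can still mean about three calendar days over a weekend, which is a further reason for the automatic message.

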### **Potential Study Benefits**

Our study will allow participants to engage with a mental health platform where they can learn skills to manage their mental health and improve their mental well-being. Additionally, through the study, we will gain a better understanding of which incentives increase engagement on a mental health platform, which can inform more effective delivery of mental health resources and information. Online mental health platforms, such as NeuroFlow, have the potential to improve wellbeing in college students, which would provide a major benefit to public health.

# Risk / Benefit Assessment

There is minimal to no risk associated with this study, and the benefits of improving college student mental health and developing an understanding of the incentives that increase mental health platform engagement and utilization is a major benefit associated with the study. Therefore, the benefits of the study outweigh any potential risks associated with the study.

# **General Attachments**

The following documents are currently attached to this item:

Additional forms (modificationform2019.6-clean\_01.doc)

Additional forms ([name].pdf)

Recruitment materials (neuroflow-flyerhorizontal.pptx)

Additional forms ([name]\_2021.pdf)

Additional forms ([name]\_2021.pdf)

Additional forms ([name]\_2021.pdf)

Additional forms ([name]\_2019\_05.pdf)

Additional forms (neuroflow-termsofservice.docx)

Additional forms (gad-7.doc)

Additional forms (phq-9.pdf)

Additional forms (who-5.pdf)

Additional forms (ders1.pdf)

Questionnaires (demographic questionnaire.doc)

Questionnaires (screenerandconsenttocontact.docx)

Recruitment materials (neuroflow-flyervertical.pptx)

Cover Letter (neuroflow-revisioncoverletter\_hn1.docx)

Informed consent form (neuroflow-consentformsfinalre2.docx)

Informed consent form (neuroflow-consentformsfinalre-trackedchanges1.docx)
